10.4.4 Assessment of Expectedness

Events considered to be unexpected or unusual in this patient population, and/or possibly related to the study drug, will be considered AEs, SAEs, ARs, SARs and SUSARs. Please also refer to Appendix 3.

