10. ADVERSE EVENTS

Investigators who are is clinically qualified at consultant level will be responsible for the detection and documentation of events meeting the criteria and definitions detailed below.

There are likely to be adverse and severe adverse events including death, in patients with sepsis, as described in Appendix 3. The Chief Investigator and the clinical team will make decisions as to whether any such events are unexpected in terms of timing or severity and considered related to the study drug, with advice from the DMC as necessary.

The only expected adverse event as a result of the IMP is drowsiness manifesting as a decrease in sedation requirements as determined using the RASS score [24,25].

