10.1 DEFINITIONS

ICU or HDU admission is a pre-requisite for study participation. AEs and SAEs as will be recorded and reported to the Sponsor within the specified time period as appropriate.

An **adverse event** (AE) is any untoward medical event affecting a clinical trial participant. Each initial AE will be considered for severity, causality or expectedness and may be reclassified as a serious event or reaction based on prevailing circumstances.

An **adverse reaction** (AR) is where it is suspected that an AE has been caused by a reaction to the trial drug

A serious adverse event (SAE), serious adverse reaction (SAR) or suspected unexpected serious adverse reaction (SUSAR) is any AE, AR or UAR that at any dose:

- results in death;
- is life threatening (i.e. the subject was at risk of death at the time of the event; it does not refer to an event which hypothetically might have caused death if it were more severe);
- requires hospitalisation or prolongation of existing hospitalisation;
- results in persistent or significant disability or incapacity;
- is a congenital anomaly or birth defect.

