10.2 DETECTING AEs AND SAEs

All AEs and SAEs will be recorded from the time of study entry until the end of the study visit, defined as 24h for Stage 1 and up to 5 days for Stage 2 whilst patients remain on the ICU/HDU.

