10.4.1 Assessment of Seriousness

The Investigators will make an assessment of seriousness as defined in Section 10.1 and whether any events are usual and expected and/or considered related to the study drug, with advice from the DMC as necessary. Please also refer to Appendix 3.

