10.4.2 Assessment of Causality

The Investigator will make an assessment of whether the AE/SAE is likely to be related to treatment according to the following definitions:

Unrelated: where an event is not considered to be related to the study drug.

Possibly: although a relationship to the study drug cannot be completely ruled out, the nature of the event, the underlying disease, concomitant medication or temporal relationship make other explanations possible.

Probably: the temporal relationship and absence of a more likely explanation suggest the event could be related to the study drug.

Definitely: The known effects of the study drug or its therapeutic class, or based on challenge testing, suggest that study drug is the most likely cause.

All AEs/SAEs judged as having a reasonable suspected causal relationship (e.g. possibly, probably, definitely) to the study drug will be considered as ARs/SARs. All AEs/SAEs judged as being related (e.g. possibly, probably, definitely) to an interaction between the study drug and another drug will also be considered to be AR/SAR.

Alternative causes such as natural history of the underlying disease and other risk factors and the temporal relationship of the event to the treatment in these critically ill patients will be considered. Please also refer to Appendix 3.

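### Section 10.4.4 does not fit the protocol's own AE and AR definitions, and expectedness is judged against sepsis although drowsiness is the only event expected from melatonin

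*Protocol*

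**What the plan says.** **Definitions and recording.** Section 10.1 states that an adverse event "is any untoward medical event affecting a clinical trial participant". Assessment comes afterwards: "Each initial AE will be considered for severity, causality or expectedness". An adverse reaction is an AE that the drug is suspected of having caused. Section 10.2 sets the recording rule: "All AEs and SAEs will be recorded from the time of study entry until the end of the study visit". Section 10.5 sends SAEs to the sponsor within 24 hours. Neither 10.2 nor 10.5 exempts sepsis complications.

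**Causality.** Section 10.4.2 has a class for events without a drug link ("Unrelated: where an event is not considered to be related to the study drug"). AEs and SAEs with a reasonable suspicion of causation "to the study drug will be considered as ARs/SARs".

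**Expectedness.** Section 10.4.4 says that events "unexpected or unusual in this patient population, and/or possibly related to the study drug, will be considered AEs, SAEs, ARs, SARs and SUSARs", and points to Appendix 3. Section 10.4.1, although headed as seriousness, also asks "whether any events are usual and expected and/or considered related to the study drug" and points to the same appendix. The introduction to section 10 says: "There are likely to be adverse and severe adverse events including death, in patients with sepsis, as described in Appendix 3". It then asks the Chief Investigator and clinical team whether such events are out of the ordinary in timing or severity and thought to be drug-related. The same introduction names drowsiness as the only adverse event expected from the IMP.

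**Other places.** Section 6.1.6 says there is no SmPC. Section 12.6.1 says no serious side effects of melatonin have been reported. Section 10.6 ties the 7- and 15-day regulatory reports to SUSAR status.

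**The concern.** There are two separate problems.

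First, 10.4.4 is headed as an assessment of expectedness, but it states which events receive the labels AE, SAE, AR, SAR and SUSAR. Those labels are already defined in 10.1 and 10.4.2 on other grounds, so staff could classify the same event differently depending on which subsection they follow.

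Second, whether a serious reaction is expected should turn on what is known of the drug. The three places that set the test measure it against the disease instead. This matters because 10.6 expedites only SUSARs, and because section 12.3 has the DMC advise on termination according to the severity of unexpected adverse events. The draft DMC charter notes that high repeated doses have not been given to patients with sepsis before. Drug harm that resembles a sepsis complication is therefore the kind of signal a sepsis-based standard would be slow to separate out.

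**Working it through.** No figure in the protocol is at issue. The check compares the subsections and makes a few counts.

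**Step 1: 10.4.4 against 10.1, 10.2 and 10.4.2.** Take a serious event and cross its sepsis expectedness with its relation to the drug.

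| Serious event | Under 10.1, 10.2, 10.4.2 | 10.4.4 read as the test for what counts | 10.4.4 read as a sufficient condition |
|---|---|---|---|
| On Appendix 3, unrelated (e.g. renal failure needing RRT) | SAE, not SAR | Neither AE nor SAE: **conflict** | Sentence silent; SAE by 10.1 |
| Not on Appendix 3, unrelated | SAE, not SAR | Falls within a list that includes AR, SAR and SUSAR: **conflict** | Same: **conflict** |
| On Appendix 3, possibly related (e.g. arrhythmia) | SAR | Falls within the list, SUSAR included | Same |
| Not on Appendix 3, possibly related | SAR | Falls within the list | Same |

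The missing word *only* therefore does not rescue the sentence. With it, the first row fails. Without it, the second row still fails, because *and/or* admits events that are unexpected but unrelated.

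**Step 2: the standard for expectedness.** In the third row, whether the SAR is a SUSAR depends on whether it is expected.

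- By the drug standard in the section 10 introduction, only drowsiness is expected, so a related arrhythmia is unexpected and 10.6 applies.
- By Appendix 3, to which 10.4.1 and 10.4.4 refer, arrhythmia is expected. The introduction's timing-or-severity question could bring some such events back, but it too measures them against the usual course of sepsis.

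**Step 3: counts.**

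- Appendix 3 entries: 4 cardiovascular + 2 respiratory + 2 nervous + 3 gastro-intestinal + 3 renal + 2 general = 16. Drowsiness is not among them.
- Section 10 refers to Appendix 3 in five places (introduction, 10.4, 10.4.1, 10.4.2, 10.4.4) and to the Investigator Brochure in none.
- Section 6.4 gives three examples of an unexpected reaction to melatonin (vomiting, diarrhoea, anaphylaxis). One of the three, diarrhoea, is on Appendix 3.

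These counts show where the investigator is sent. They do not measure how many events would be misclassified.

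**The case against.** **Full recording is the dominant message.** A reader might infer that the protocol exempts expected sepsis complications from safety recording. The documents do not support that. Section 10.4.4 does not say *only*, and it sits among assessment rules rather than definitions. Sections 10.1, 10.2 and 10.5 make no exemption, and 6.4 and the introduction to section 10 themselves call Appendix 3 events adverse events. This stands, and it makes the exclusive reading the weaker one.

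**The sentence itself errs towards over-reporting.** A reader might also infer that 10.4.4 removes related sepsis-type events from SUSAR reporting. Taken literally it does the opposite: a possibly related event satisfies *and/or*, and the labels listed include SUSAR. This stands too. The risk of a missed report comes from the Appendix 3 pointers and from the introduction's sepsis-based test.

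**The list of labels may be shorthand.** The sentence does not mention seriousness, so it cannot mean that every event gets all five labels. It may mean whichever label fits. On that view it adds nothing to 10.1 and 10.4.2, and it still does not say which condition leads to which label.

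**The drug standard is stated, and 6.4 uses it.** Drowsiness is named at the start of section 10. Diarrhoea in 6.4 might look like a contradiction, but that passage concerns a reaction attributed to melatonin. Treating it as unexpected although sepsis also causes diarrhoea is largely the right distinction. What remains is that 10.4.1 and 10.4.4 do not apply it.

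**Safeguards.** Consultant-level investigators at the one named hospital classify events. The DMC comments on the expected-event list and the AE strategy before recruitment, and sees data after every 10 Stage 2 patients. The Investigator Brochure (cited in 1.1, 1.2, 6.1 and Appendix 1) and the SOPs may hold reference safety information. These reduce the risk without correcting the text, since 10.4.1 and 10.4.4 send the investigator to neither document.

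**Conclusion.** The point holds as an internal inconsistency in the safety rules. On either reading that gives 10.4.4 any effect, it disagrees with at least one of 10.1, 10.2 and 10.4.2. Independently, the protocol names a drug-based expectation and then directs the judgement to a disease-based list, so a related serious event on that list could be called expected and not expedited.

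The size is minor to moderate. No effect can be quantified: the protocol gives no rates for Appendix 3 events, no share judged related, and no indication of how staff will read 10.4.4. It does not establish that any event would in practice go unrecorded or unreported. The conclusion rests on the text shown and assumes that the Brochure and SOPs do not already override it. Sample size and error rates are unaffected.

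**What to change.** Rewrite 10.4.4 to keep the three judgements apart:

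- (a) All untoward events, including those on Appendix 3, are recorded as AEs or SAEs under 10.1 and 10.2.
- (b) Only events judged possibly, probably or definitely related are ARs or SARs, under 10.4.2.
- (c) A SAR is a SUSAR unless it is expected for the IMP, judged against drowsiness and the Investigator Brochure. Appendix 3 serves only as background for the causality judgement.

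Align the wording of 10.4.1 and the timing-or-severity sentence in the introduction to section 10. Leave the 24-hour SAE reporting in 10.5 as it is. Rule (c) agrees with the diarrhoea example in 6.4.

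The cost is a wording amendment in three places, slightly more AE data entry, and possibly a few more expedited reports.

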10.5 REPORTING OF SAEs / SARs / SUSARs

Once the Investigator becomes aware that an SAE has occurred in a study participant, they will report the information to the Sponsor within 24h of becoming aware of the event as per the current SOP. The SAE form will be completed as thoroughly as possible

with all available details of the event, signed by the Investigator or their delegate. If all the required information is not available at the time of reporting, the Investigator will ensure that any missing information is provided as soon as this becomes available. It will be indicated on the report that this information is follow-up information of a previously reported event.

10.6 REGULATORY REPORTING REQUIREMENTS

An annual Development Safety Update Report (DSUR) will be submitted to the MHRA and the main REC listing all SARs and SUSARs. The Chief Investigator is responsible for submitting annual DSURs to the MHRA and the main REC on the anniversary of the Clinical Trial Authorisation approval.

The Chief Investigator is responsible for informing the MHRA and the main REC of these safety issues. Fatal or life threatening SUSARs will be reported to MHRA no later than **7 calendar days** and all other SUSARs will be reported no later than **15 calendar days** after they are first aware of the reaction.

10.7 FOLLOW UP PROCEDURES

After initially recording an AE or recording and reporting an SAE, the Investigator will follow each participant as per the current SOP. As detailed in the protocol, AEs and SAEs will be followed up whilst the patient remains on ICU, for a maximum of 24h for Stage 1 and 5d for Stage 2. SUSARs will be followed up until resolution as per the SOP.

11. PREGNANCY

Pregnant subjects will be excluded, and it is very unlikely that a patient will become pregnant whilst admitted to the ICU.

12. TRIAL MANAGEMENT AND OVERSIGHT ARRANGEMENTS

12.1 TRIAL STEERING GROUP

A Trial Management Group consisting of the study team members and 3 independent members including one lay member will have oversight of the trial conduct. It will be Chaired by an independent Intensive Care Clinician ([name], Leeds) as per the current SOP. The group will meet at least annually.

12.2 PROJECT MANAGEMENT GROUP

The trial will be managed on a day to day basis by the project management group (Appendix 4). The Chief Investigator or delegated personnel will be responsible for checking the CRFs for completeness, plausibility and consistency. Any queries will be resolved by the Investigator or delegated member of the trial team.

A Delegation Log will detail the responsibilities of each member of staff working on the trial.

12.3 DATA MONITORING COMMITTEE

An independent Data Monitoring Committee (DMC) will be established to oversee the safety of subjects in the trial and will comprise of 3 consultants in intensive care who are external to Aberdeen . The terms of reference of the DMC and the names and contact details of the Chair are detailed in Appendix 5. The DMC will be provided with data after Stage 1 and after each 10 patients are randomised to Stage 2. The data provided will be blinded. No data will be unblinded (unless requested for safety concerns), until the end of the study, unless emergency unblinding is required. The DMC will agree terms of reference and other procedures prior to the study starting. The DMC will monitor the trial data in 'virtual' meetings after Stage 1 and after every 10 patients randomised to

Stage 2 and be regularly provided with all relevant data. The DMC will make recommendations as to any modifications that are required to be made to the protocol and advise on study termination if they are of the opinion the severity of unexpected adverse events in the study population is unacceptable. If the DMC has safety concerns and request data to be unblinded, a third party will oversee unblinding.

12.4 INSPECTION OF RECORDS

Principal Investigators and institutions involved in the study will permit trial related monitoring, audits, REC review, and regulatory inspection(s). In the event of an audit, the Investigator agrees to allow the Sponsor, representatives of the Sponsor or regulatory authorities direct access to all study records and source documentation.

12.5 STUDY MONITORING

A monitor, designated by the Sponsor, or an appointed local monitor will visit the Aberdeen study site prior to the start of the study, during the course of the study and will undertake a close down visit at study end.

The trial will be monitored by NHS Grampian. We will comply fully with the University of Aberdeen/NHS Grampian joint standard operating procedures (SOPs) for reporting of serious adverse events to sponsors, the MRHA, the NHS R&D director and the research ethics committee.

12.6 RISK ASSESSMENT

An independent risk assessment has been carried out by the sponsor.

12.6.1 Potential Risks

There have been no reports of serious side effects in patients receiving melatonin [15,17,18]. Non-serious side effects are limited to transient drowsiness [18].

12.6.2 Minimising Risk

Risk minimisation strategies:

- 1. DMC approval after each dose cohort in Stage 1.
- 2. Stage 1 is open label.
- 3. DMC will approve continuation after each cohort of 10 patients in Stage 2.

13. GOOD CLINICAL PRACTICE

13.1 ETHICAL CONDUCT OF THE STUDY

The study will be conducted in accordance with the principles of good clinical practice (GCP).

A favourable ethical opinion will be obtained from the appropriate REC and local NHS R&D approval will be obtained prior to commencement of the study.

13.2 REGULATORY COMPLIANCE OF THE STUDY

The study will not commence until a Clinical Trial Authorisation (CTA) is obtained from the appropriate Regulatory Authority. The protocol and study conduct will comply with the Medicines for Human Use (Clinical Trials) Regulations 2004, and any relevant amendments.

13.3 INVESTIGATOR RESPONSIBILITIES

The Chief Investigator is responsible for the overall conduct of the study at the site and compliance with the protocol and any protocol amendments. In accordance with the principles of GCP, the following areas listed in this section are also the responsibility of the Investigator. Responsibilities may be delegated to an appropriate member of study site staff. Delegated tasks will be documented on the Delegation Log and signed by all those named on the list.

13.3.1 Informed Consent

The Investigator is responsible for ensuring informed consent is obtained before any protocol specific procedures are carried out. The decision of a participant to participate in clinical research is voluntary and should be based on a clear understanding of what is involved.

Participants or legal representatives will receive adequate oral and written information – appropriate Participant Information and Informed Consent Forms will be provided. The oral explanation to the participant or their legal representative will be performed by the Investigator or designated person and will cover all the elements specified in the Participant Information Sheet/Informed Consent.

The participant or their legal representative will be given every opportunity for clarification of any points they do not understand and, if necessary, ask for more information. The participant/legal representative will be given sufficient time to consider the information provided. It will be emphasised that consent may be withdrawn at any time without loss of benefits to which they otherwise would be entitled.

The participant/legal representative will be informed and agree to study records being inspected by regulatory authorities but understand that inspection is undertaken by authorised personnel and their data will remain confidential.

The Investigator or delegated member of the trial team and the participant/legal representative will sign and date the Informed Consent Form(s) to confirm that consent has been obtained. The participant/legal representative will receive a copy of this document and a copy will be filed in the patient's notes and the Trial Master File (TMF).

13.3.2 Study Site Staff

The Investigator will be familiar with the IMP, protocol and the study requirements. The Investigator will ensure that all staff assisting with the study are adequately informed about the IMP, protocol and their trial related duties.

13.3.3 Data Recording

The Investigator is responsible for the quality of the data recorded in the CRF.

13.3.4 Investigator Documentation

Prior to beginning the study, each Investigator will be asked to provide particular essential documents to the Sponsor, including but not limited to:

- An original signed Investigator's Declaration (as part of the Clinical Trial Agreement documents);
- A signed copy of the Chief Investigator's responsibilities letter issued by the Sponsor.

The Chief Investigator, with the agreement of the Sponsor, will ensure all other documents required for compliance with the principles of GCP are retained in a TMF and that appropriate documentation is available in local ISFs.

13.3.5 GCP Training

Where appropriate all relevant research staff will have GCP training or will undergo GCP training. A training log will be kept in the Trial Master File.

13.3.6 Confidentiality

All laboratory specimens, evaluation forms, reports, and other records will be identified in a manner designed to maintain participant confidentiality. All records will be kept in a locked filing cabinet in a locked office only accessed by the Principal Investigator. Clinical information will not be released without the written permission of the participant, except as necessary for monitoring and auditing by the Sponsor, its designee, Regulatory Authorities, or the REC. The Investigator and study site staff involved with this study will not disclose or use for any purpose other than performance of the study, any data, record, or other unpublished, confidential information disclosed to those individuals for the purpose of the study. Prior written agreement from the Sponsor or its designee will be obtained for the disclosure of any said confidential information to other parties.

13.3.7 Data Protection

All Investigators and study site staff involved with this study will comply with the requirements of the Data Protection Act 1998 with regard to the collection, storage, processing and disclosure of personal information and will uphold the Act's core principles. Access to collated participant data will be restricted to those clinicians treating the participants.

Computers used to collate the data will have limited access measures via user names and passwords.

Published results will not contain any personal data that could allow identification of individual participants.

14. STUDY CONDUCT RESPONSIBILITIES

14.1 PROTOCOL AMENDMENTS

Any changes in research activity, except those necessary to remove an apparent, immediate hazard to the participant, must be reviewed and approved by the Sponsor. Amendments to the protocol will be submitted in writing to the appropriate REC, Regulatory Authority and local R&D for approval prior to participants being enrolled into an amended protocol.

